5.7.6 Pulmonary Function Tests (PFTs)

The actual value and change from baseline to each visit will be descriptively summarized (mean, median, standard deviation, min, max) for PFTs by visit in safety analysis set.

Statistical Analysis Plan of PTCL (Version 3.0)

Protocol Code: DZ2019J0005 (Part B)

Date: Mar 25, 2023

The number and percentage of participants with abnormal FEV1PP and DLCO decrease (worst case) meeting each criterion below will be reported respectively. Only the post-baseline data will be included for analysis.

- FEV1PP
 - $\geq 70\%$ and $\leq 99\%$
 - $\geq 60\%$ and $< 70\%$
 - $\geq 50\%$ and $< 60\%$
 - $< 50\%$
- DLCO decrease from baseline
 - ≥ 3 and ≤ 5 (ml/min/mmHg)
 - > 5 and ≤ 8 (ml/min/mmHg)
 - > 8 (ml/min/mmHg)

All the PFTs measurements will be listed in the individual data listing.

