- 4. Patients with severely decreased lung function (i.e. any parameter of FEV1, and DLCO < 60% of predicted value). Past medical history of pneumonitis, drug-induced interstitial lung disease, radiation pneumonitis which required steroid treatment, or any evidence of clinically active interstitial lung disease.
- 5. Patients with disease condition which requires the treatment of immunosuppressants, biologics, or NSAIDs (non-steroid anti-inflammatory drugs).
- 6. Active infections including:

- History of known latent or active tuberculosis (TB), e.g. signs of active or latent TB on PPD test or chest X-ray/CT, skin test showing an induration of >10 mm or more, or positive results of screening tests according to local recommendations.
- Known infection with human immunodeficiency virus (HIV), or serologic status reflecting active hepatitis B or hepatitis C infection as follows:

	Inclusion	Exclusion
HIV antibody	Negative	Positive
HCV antibody	Negative	Positive
HBV	Both HBsAg and HBcAb are negative	Either HBsAg or HBcAb is positive

- Active viral infections (i.e. zoster) other than hepatitis B or C.
- Infections requiring oral or intravenous antimicrobial therapy or interferon.
- Bacterial infections including pneumonia within 30 days.
- 7. Any of the following cardiac criteria:
 - Congestive heart failure (CHF) per New York Heart Association (NYHA) classification > Class II (see Appendix I).
 - Clinically significant valvular diseases, hypertrophic or constrictive cardiomyopathy.
 - Any clinically significant abnormalities in rhythm, conduction or morphology of resting ECG, e.g., complete left bundle branch block, third degree heart block, and second-degree heart block, PR interval > 250 msec.
 - Cardiac ventricular arrhythmias requiring anti-arrhythmic therapy.
 - Acute Myocardial Infarction (AMI) within 6 months prior to starting treatment, unstable angina or new-onset angina.
 - Patients with heart transplant.
 - Mean resting corrected QTcF interval (QT_C) > 450 ms on screening triplicate electrocardiogram (ECG).
 - Patients with factors that increase the risk of QT prolongation or arrhythmic events (e.g., heart failure, hypokalaemia, congenital long QT syndrome, any concomitant medication known to prolong the QT interval (Appendix II)) or family history of long QT interval syndrome or unexplained sudden death under 40 years of age in first degree relatives).

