6.4.5 Other safety assessments

Echocardiogram/MUGA Scan

Echocardiogram or MUGA scan to assess LVEF will be conducted at screening (prior to first dose of AZD4205), Cycle 3 Day 1, then every 12 weeks for the rest of cycle. Additional Echocardiogram or MUGA scan will be performed whenever necessary as clinically indicated throughout the study.

The modality of the cardiac function assessments must be consistent within a patient i.e. if echocardiogram is used for the screening assessment then echocardiogram should also be used for subsequent scans if required. The patients should also be examined using the same machine and operator whenever possible, and a quantitative measurements should be taken. Recommendations include having complete high quantity standardized 2-D with Doppler echocardiographic examinations performed by an experienced sonographer and include evaluation of both systolic and diastolic left ventricular function. Ejection fraction determinations should be determined quantitatively based on bi-plane measurements of end diastolic and end systolic left ventricular volumes.

An asymptomatic LVEF decrease to < 40% or LVEF [40-54%] and LVEF decrease \ge 10% from baseline or any symptomatic LVEF decrease are the dose interruption criteria. Any symptomatic decrease in LVEF will prompt the discontinuation of the treatment and a cardiac consultation.

Pulmonary function tests (PFTs)

Signs and symptoms (cough, short breath and pyrexia, etc) including auscultation for lung field will be checked at each visit.

PFTs (including spirometry and DLCO) will be performed at screening, Cycle 3 Day 1 and then every 6 weeks and whenever clinically indicated.

HRCT scan will be performed when clinically indicated (see below, details could be found in Appendix VII. Guidance for the Safety Monitering and Management of Adverse Events):

- If new or worsening pulmonary symptoms (e.g., dyspnea) or radiological abnormality suggestive of interstitial lung disease on CT scan or decrease in lung function tests (DLCO decrease ≥ 15%) is observed, the study treatment dosing should be interrupted and a full diagnostic workup (including chest X-Ray with PA and lateral view, cardiac, infectious and hematological workups) will be performed. A full diagnostic workup is strongly recommended to exclude alternative causes such as infection, disease progression and cardiac causes. Alternative clinical diagnosis will be managed according to local practice.

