5.7.5 Echocardiogram/MUGA Scan

The actual value and change from baseline to each visit will be descriptively summarized (mean, median, standard deviation, min, max) for echocardiogram/MUGA scan by visit in the safety analysis set.

The number and percentage of participants with abnormal LVEF decrease (worst case) meeting each criterion below will be reported respectively. Only the post-baseline data will be included for analysis.

- Absolute value $>50\%$
 - Decrease from baseline $\geq 10\%$ and $<20\%$
 - Decrease from baseline $\geq 20\%$
- Absolute value $\geq 40\%$ and $\leq 50\%$
 - Decrease from baseline $\geq 10\%$ and $<20\%$
 - Decrease from baseline $\geq 20\%$
- Absolute value $\geq 20\%$ and $<40\%$
 - Decrease from baseline $\geq 10\%$ and $<20\%$
 - Decrease from baseline $\geq 20\%$
- Absolute value $<20\%$
 - Decrease from baseline $\geq 10\%$ and $<20\%$
 - Decrease from baseline $\geq 20\%$

All the LVEF measurements and change from baseline will be listed in the individual data listing.

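### The SAP's worst-value FEV1PP rows do not isolate on-treatment decline, and its DLCO and LVEF rows do not line up with the protocol's own thresholds

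*SAP*

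**What the plan says.** SAP 5.7.6 plans a worst-case table: "The number and percentage of participants with abnormal FEV1PP and DLCO decrease (worst case) meeting each criterion below will be reported respectively". Only post-baseline data enter it. Two sets of rows follow.

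- **FEV1PP:** 70–99%, 60–<70%, 50–<60% and <50% of predicted. These are levels; baseline is not mentioned.
- **DLCO decrease from baseline:** 3–5, >5–8 and >8 mL/min/mmHg. These are absolute falls.

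SAP 5.7.5 does the same for LVEF, counting "participants with abnormal LVEF decrease (worst case) meeting each criterion below". The level cuts are 50%, 40% and 20%, and each level is split into falls of 10–<20 and of 20 or more.

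The protocol uses different cuts.

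- Section 4.2, item 4 excludes at entry "any parameter of FEV1, and DLCO < 60% of predicted value".
- Section 6.4.5 says that if a "decrease in lung function tests (DLCO decrease ≥ 15%) is observed, the study treatment dosing should be interrupted". Appendix VII repeats the 15% figure. Neither says whether it is relative or in points of percent predicted.
- Sections 5.2.2 and 6.4.5 name an asymptomatic LVEF below 40%, an LVEF of 40–54% with a fall of at least 10%, and any symptomatic fall.
- The Appendix VII table for asymptomatic falls adds cuts at 55% and at a fall of 15%.
- Section 4.1 requires LVEF of at least 55% at entry.

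**The concern.** Lung and cardiac effects are named risks in protocol 5.2.2, and Part B is meant to support a marketing application. A reader of these tables will want to know how many patients got worse on treatment and how many crossed a line the protocol cares about.

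The FEV1PP rows mix pre-existing reduced function with new decline. Taking the worst of repeated tests (Cycle 3, then every 6 weeks) also pulls values down through measurement noise alone. No DLCO row counts the 15% criterion. The LVEF rows put patients in different protocol categories into one cell. With a single arm there is no control group against which to judge a high count.

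**Working it through.** **1. Unit for LVEF falls.** The footnote to the Appendix VII table says that a fall of more than 15% ending above 55% needs a start above 70%. In percentage points, 55 + 15 = 70, which reproduces it. As a relative fall, 55 / 0.85 = 64.7, which does not. Protocol LVEF falls are therefore read as points.

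**2. FEV1PP.** Example patients, all eligible at 60% or more:

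| Baseline → worst | Change | SAP row |
|---|---|---|
| 85 → 85 | 0 | 70–99 |
| 75 → 90 | +15 | 70–99 |
| 65 → 65 | 0 | 60–<70 |
| 65 → 58 | −7 | 50–<60 |
| 130 → 100 | −30 | none |

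The two upper rows can be filled with no fall, or after a rise. The two lower rows require a fall, because nobody eligible starts below 60.

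For size, the documents give no baseline distribution, so one is assumed: normal, mean μ, SD 15, truncated at 60. With no change in any patient, the share in the 60–99% range is

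[Φ((99−μ)/15) − Φ((60−μ)/15)] / [1 − Φ((60−μ)/15)].

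- μ = 85: (0.825 − 0.048) / 0.952 = 0.82
- μ = 90: (0.726 − 0.023) / 0.977 = 0.72
- μ = 95: (0.605 − 0.010) / 0.990 = 0.60

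**3. DLCO.** If 15% is relative, the trigger is 0.15 × baseline, and the lowest SAP row starts at 3 units. They agree where 0.15 × baseline = 3, that is, at 20. Baselines below are assumed.

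| Baseline (mL/min/mmHg) | 15% fall in units | 3 units as % of baseline |
|---|---|---|
| 10 | 1.5 | 30% |
| 15 | 2.25 | 20% |
| 20 | 3.0 | 15% |
| 30 | 4.5 | 10% |
| 40 | 6.0 | 7.5% |

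Below 20, some falls that meet the criterion are in no row (2.25 units from 15). Above 20, some falls that do not meet it are counted (3 units, or 10%, from 30). If 15% means points of percent predicted, no row corresponds to it either.

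**4. LVEF.** First, is anyone lost? An asymptomatic eligible patient meets a protocol threshold by one of three routes: 40–54% with a fall of at least 10 points; 55% or more with a fall above 15; or below 40%, which from 55% or more is a fall above 15. All need a fall of at least 10, so all land in some SAP row.

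Second, are categories kept apart? Three patients in the single cell for LVEF above 50% with a fall of 10–<20:

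| Baseline → worst | Fall | Appendix VII category |
|---|---|---|
| 72 → 60 | 12 | continue |
| 64 → 52 | 12 | interruption |
| 70 → 54 | 16 | discontinue |

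Over all integer pairs with baseline 55–80 (upper end assumed) and a later value from 10 up to baseline, the pooled cells are as follows. These count possible pairs, not expected patients.

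| SAP cell | Continue | Interrupt | Discontinue |
|---|---|---|---|
| >50, fall 10–<20 | 81 | 58 | 16 |
| >50, fall ≥20 | 0 | 21 | 34 |
| 40–50, fall 10–<20 | 0 | 51 | 44 |
| In no row | 260 | 0 | 0 |

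**The case against.** The heading of the lung-function table can be read as two items, abnormal FEV1PP and a decrease in DLCO, and the bullet labels fit that reading. On it, FEV1PP is simply a worst level, and nobody is called a decliner. Some ECG rows in SAP 5.7.3, such as QRS above 120 msec, are also plain levels. Neither document says these tables exist to count protocol criteria, and the protocol's only FEV1-specific criterion belongs to DLT-like events in Part A dose escalation.

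Other outputs carry part of the load. SAP 5.7.6 also says: "The actual value and change from baseline to each visit will be descriptively summarized (mean, median, standard deviation, min, max) for PFTs by visit". All PFT values, and all LVEF values and changes, are listed. SAP 5.7.1 tabulates adverse events leading to interruption, reduction and discontinuation.

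Much of this stands. A reader might infer that the safety counts will be wrong. They will not be: they are correct for the rows as defined. A reader might also infer that no FEV1PP row needs a decline, or that the LVEF table misses patients who met a threshold. The 60% entry rule rules out the first for the two lower rows, and step 4 rules out the second for asymptomatic patients.

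What does not stand is that the other outputs close the gap. By-visit summaries do not count patients who cross a line. Adverse-event tables show actions taken, not criteria met. Even as a plain level, an upper FEV1PP row cannot tell old impairment from new. Laboratory grades, blood pressure and ECOG all get baseline-to-worst shift tables in the same SAP, and the PR and heart-rate rows require a change from baseline.

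**Conclusion.** The point holds as a weakness of three descriptive displays.

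- **FEV1PP:** the 70–99% and 60–<70% rows do not show on-treatment worsening. The 60–82% range rests wholly on the assumed baseline distribution; the structural point needs only the 60% entry rule.
- **DLCO:** no row counts the protocol's 15% criterion. The two-way misclassification around a baseline of 20 assumes that 15% is relative.
- **LVEF:** the rows pool protocol categories because they cut at 50% and 20 points, not at 54/55% and 15 points. That no asymptomatic patient is lost rests on reading protocol falls as points. A symptomatic fall of under 10 points meets a protocol criterion but enters no row.

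The SAP names protocol version 5.0 as its basis, while the protocol reviewed here is version 6.0. The comparison is with the current text. No test, endpoint, alpha or power figure depends on any of this.

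**What to change.** All three changes are to reporting only; no clinical rule is altered.

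1. **FEV1PP:** replace the level rows with a baseline-to-worst category shift table, or count a patient only when the worst category is below the baseline category. Add a category above 99%, so that falls from high baselines are placed.
2. **DLCO:** add a row for a decrease of at least 15% from baseline, and state whether that is relative or in points of percent predicted. The unit should be taken from a clarified protocol.
3. **LVEF:** add rows at the protocol's cut points, 54/55% and a 15-point fall, and state that falls are in percentage points. A split at 55% alone is not enough, because the 15-point cut would still be hidden inside the 10–<20 rows.

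The cost is a few table rows from data already collected. One check is needed: SAP 4.3.8 lists DLCO only in absolute units, so a percent-predicted version of the 15% row would need that variable added to the analysis data.

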5.7.7 Physical Examination and ECOG

Shifts from baseline ECOG scale to post-baseline scale (worst case) will be tabulated in the safety analysis set.

All the ECOG measurements will be listed in the individual data listing.

Abnormal physical examination data will be provided in by-participant listings.

6. INTERIM ANALYSES

No interim analysis will be performed for this study.

7. DATA HANDLING RULES

7.1 Time Points and Visit Windows

Day 1 is defined as the day of first dose of investigational product. Relative days after Day 1 are calculated as (assessment date – Day 1 date) + 1. Relative days prior to Day 1 are calculated as (assessment date – Day 1 date). The day prior to Day 1 is Day -1.

The baseline value is defined as the most recent non-missing value before the first dose of investigational product. The data measured on Day 1 will be considered as candidate of baseline, unless there is information indicating that the data are measured after the dosing.

Statistical Analysis Plan of PTCL (Version 3.0)

Protocol Code: DZ2019J0005 (Part B)

Date: Mar 25, 2023

In by-visit summary, all post-baseline data will be analysed using nominal study visits as defined in the Study Schedule and CRF. No visit windows will be applied for summary and analysis and only data from scheduled visits will be included in the summary.

Analysis period is defined as the time from date of first dose to 28 days after last dose or the day prior to the subsequent anti-cancer therapy initiation after treatment discontinuation (including participation in a new clinical trial), whichever is earlier. Analysis period will be used in the safety summaries that require consideration of both scheduled and unscheduled visit data (e.g., summary of post-baseline worse case, etc.).

7.2 Handling of Missing Data and Outliers

The imputation rule for partial/missing dates of AE and prior/concomitant medication (CM) is listed below. End date will be imputed first and start date will be imputed based on the imputed end date. If year of the date is missing, the date will be considered as totally missing and imputed accordingly.

The figure consists of a 3x3 grid of 9 horizontal bar charts. Each chart has a black vertical axis on the left and a black horizontal axis at the bottom. The bars are black and vary in length. The first chart in the top row has a very long bar. The second chart in the top row has a short bar. The third chart in the top row has a very long bar. The first chart in the middle row has a short bar. The second chart in the middle row has a very long bar. The third chart in the middle row has a very long bar. The first chart in the bottom row has a short bar. The second chart in the bottom row has a very long bar. The third chart in the bottom row has a short bar.

Statistical Analysis Plan of PTCL (Version 3.0)

Protocol Code: DZ2019J0005 (Part B)

Date: Mar 25, 2023

9. APPENDIX

Appendix A Visit Schedule (Part B of Study)

Study Cycles (21 days for one cycle)	Screen ^A	C1	C2	C3	C4	C5	C6	C7	C8	C9	C10 onwards	End of treatment	28-day Follow-up ^B	Post progression survival F/T ^C
Day	-28 to -1	1	8	15	1	1	1	1	1	1	1	1	1	3 monthly relative to progression
Informed consent	X													
Medical history and demographics	X	X												
Inclusion/exclusion criteria	X													
Physical examination	X	X	X	X	X	X	X	X	X	X	X	X	X	
ECOG PS	X	X	X	X	X	X	X	X	X	X	X	X	X	
Vital Signs (BP/HR)	X	X*	X	X*	X*	X	X	X	X	X	X	X	X	
Body temperature	X	X	X	X	X	X	X	X	X	X	X	X	X	
Height	X													
Weight	X	X	X	X	X	X	X	X	X	X	X	X	X	
HBV, HCV, HTV screening ^D	X													
TB screening (PPD test or X-ray/CT)	X													
Brain MRI	X													
Pulmonary Function Tests ^E	X					X		X						
Concomitant medications	X	X	=	=	=	=	=	=	=	=	=	X	X	
AE evaluation ^F	X	X	=	=	=	=	=	=	=	=	=	X	X	
12-lead ECG	X	X*	X	X*	X*	X	X	X	X	X	X	X	X	
Echocardiogram/MTU GAG	X					X								

Statistical Analysis Plan of PTCL (Version 3.0)

Protocol Code: DZ2019J0005 (Part B)

Date: Mar 25, 2023

Study Cycles (21 days for one cycle)	Screen ^A	C1	C2	C3	C4	C5	C6	C7	C8	C9	C10 onwards	End of treatment	28-day Follow-up ^B	Post progression survival F/UC
Day	-28 to -1	1	8	15	1	1	1	1	1	1	1	1	1	3 monthly relative to progression
Hematology ^H	X	X	X	X	X	X	X	X	X	X	X	X	X	
Serum chemistry ^H	X	X	X	X	X	X	X	X	X	X	X	X	X	
Coagulation ^H	X	X	X	X	X	X	X	X	X	X	X	X	X	
Urinalysis ^H	X	X	X	X	X	X	X	X	X	X	X	X	X	
Pregnancy test (pre-menopausal females only)	X													
Tumor sample for pathology confirmation ^I	X													
Plasma PK ^J	X*	X	X*	X	X*	X	X	X	X	X	X	X	X	
Whole blood for ex vivo pSTAT ^K	X*	X	X											
Blood sample for pharmacogenetics research (optional) ^L	X													
CT Scan (with contrast unless contraindicated) ^M	X													
PET ^N	X													
Bone marrow aspiration and biopsy ^O	X													
AZD4205 administration ^P	X	=	=	=	=	=	=	=	=	=	=	=	=	
Survival ^C														X

Footnote for Schedule of Study Activities (Part B):

* Multiple time points. Details can be found in corresponding sections.

A. Screening tests should be performed within 28 days before the first administration of study drug.

B. A safety follow up visit will occur 28 days (± 7) from the last dose of study drug.

Statistical Analysis Plan of PTCL (Version 3.0)

Protocol Code: DZ2019J0005 (Part B)

Date: Mar 25, 2023

- C. In the Phase 2 expansion, following disease progression, the patient, patient's family, or the patient's current physician must be contacted every 3 months for survival information, for collection of details of subsequent treatment regimens received following withdrawal from study drug and to follow up unresolved AEs (unless the patient withdraws consent) regardless of date of last contact.
- D. Both HBsAg and HBcAb should be negative for eligibility.
- E. PFTs (including spirometry and DLCO) will be performed at screening, Cycle 3 Day 1 and then every 6 weeks and whenever clinically indicated.
- F. AEs will be collected and recorded in CRF from first dosing of AZD4205 until the end of the follow up period (28 ± 7 days post last dose). However, SAE should be recorded in CRF from ICF signing to the end of defined follow-up period.
- G. Echoangiogram or MUGA scan to assess LVEF will be conducted at screening (prior to first dose of AZD4205), Cycle 3 Day 1, then every 12 weeks for the rest of cycle.
- H. In the Phase 2 expansion, laboratory tests for screening should be performed within 7 days prior to the planned first dosing date. In addition, laboratory tests do not need to be repeated at baseline if the baseline visit is within 3 days of the screening sample.
- I. In the Phase 2 expansion, submission of the tumor block or unstained slides from a diagnostic biopsy is required for retrospective central confirmation of disease histologic subtype. The diagnostic specimen needs to be from a malignant lymph node or extra-nodal tissue obtained by excisional biopsy.
- J. Patients at the selected sites will be invited for intense PK study on Cycle 1 Day 1 and Cycle 2 Day 1.
- K. Blood sampling for pSATA₅ inhibition of blood cells is only mandatory for patients enrolled in the designated sites.
- L. Blood sampling for pharmacogenetics research at screening is optional for patients enrolled in the Part B.
- M. Pre-treatment tumor assessment should be performed within 28 days prior to (preferably close to) the first dose, including a computed tomography (CT) scan (with contrast unless contraindicated) of the neck, chest, abdomen, and pelvis and any other disease sites (e.g., neck). During treatment, CT scans will be done for tumor assessments within 7 days of Day 1 of Cycle 3, 6, 9 and then every 3 cycles thereafter until PD.
- N. PET scan, where available, needs to be performed for the pre-treatment tumor assessment. During the treatment, PET should be performed on Day 1 of Cycle 3 (within 7 days) and when need to confirm a complete metabolic remission, if FDG-avid disease is detected based on baseline PET scan. Patients with confirmed CR are not required to undergo further PET scans on study unless there is suspicion of progressive disease.
- O. A bone marrow aspirate and biopsy will be done at screening (or within 60 days prior to the first dose of AZD4205). During treatment, bone marrow aspirate and biopsy will only be required to confirm any complete remission for patients with bone marrow involvement at baseline (screening) and when clinically indicated.
- P. Treatment may continue until disease progression, unacceptable toxicity, discontinuation criteria have met, withdrawal of consent or termination of the study by Sponsor. All patients need to take prophylaxis for pneumocystis carinii pneumonia (PCP) infection per European Conference on Infections in Leukemia (ECIL).

Statistical Analysis Plan of PTCL (Version 3.0)

Protocol Code: DZ2019J0005 (Part B)

[figure not shown]
Date: Mar 25, 2023

A 10x10 grid of 100 black bars of varying heights, representing a data distribution. The bars are arranged in a grid pattern, with heights ranging from very low to very high. The distribution is highly skewed, with most bars being very short and a few bars being extremely tall, particularly in the top-left and bottom-left corners.

Statistical Analysis Plan of PTCL (Version 3.0)

Protocol Code: DZ2019J0005 (Part B)

[figure not shown]
Date: Mar 25, 2023

Statistical Analysis Plan of PTCL (Version 3.0)

Protocol Code: DZ2019J0005 (Part B)

Date: Mar 25, 2023

Statistical Analysis Plan of PTCL (Version 3.0)

Protocol Code: DZ2019J0005 (Part B)

Date: Mar 25, 2023

Bin	Frequency
1	5
2	10
3	15
4	18
5	12
6	10
7	15
8	18
9	12
10	10
11	15
12	18
13	12
14	10
15	15
16	95
